APPENDIX D: REGISTRATION COVERSHEET

COH IRB# 20459: A Phase 2 Study of Acalabrutinib and PI3K δ inhibitor Umbralisib in Combination with Ublituximab (AU2) in Patients with Previously Untreated Mantle Cell Lymphoma

Data Coordinating Center:

City of Hope
[name]
[name]
[contact]
Email: [contact] (use #secure# in subject line)

Site Principal Investigator

Name:

CRA/Study Coordinator:		Contact Number:	
Patient's Initials: (F M L):		Institution: PI/ Sub-Investigator:	
Patient's DOB:		IRB approval valid until (date):	
Sex: _____ Male _____ Female		Date Informed Consent Signed:	
		Projected start date of treatment:	
Race		Ethnicity	
	Black		Hispanic
	Caucasian		Non-Hispanic
	Asian		Other _____
	American Indian	Method of Payment: _____	
	Native Hawaiian/Pacific Islander	01 Private	06 Military or Veterans Adm. sponsored
	Other _____	02 Medicare	07 Self-pay (no insurance)
		03 Medicare & private ins.	08 No means of payment (no insurance)
		04 Medicaid	09 Unknown
		05 Medicaid & Medicare	

Reason for Screen Failure:

Reason for Failing to Initiate Protocol Therapy:

APPENDIX E: PROTON PUMP INHIBITORS AND CYP3A INHIBITORS AND INDUCERS

Examples of proton pump inhibitors, and CYP3A inhibitors and inducers
Proton-pump inhibitors¹
Omeprazole, Lansoprazole, Pantoprazole, Rabeprazole, Esomeprazole, Dexlansoprazole
Strong CYP3A Inhibitors^{1,2}
Ketoconazole, Clarithromycin, Itraconazole, Nefazodone, Saquinavir, Ritonavir, Indinavir, Nelfinavir, Voriconazole, Lopinavir, Telithromycin, Conivaptan, Posaconazole, Boceprevir, Telaprevir, Cobicistat, Idelalisib, Grapefruit, Starfruit, Seville Oranges
Moderate CYP3A Inhibitors^{1,2}
Erythromycin, Verapamil, Diltiazem, Cyclosporine, Ciprofloxacin, Fluvoxamine, Fluconazole, Aprepitant, Imatinib, Nilotinib, Dronedarone, Crizotinib, Atazanavir, Letermovir, Duvelisib
Strong CYP3A Inducers^{1,2}
Phenytoin, Carbamazepine, Rifampin, Mitotane, Fosphenytoin, St John's Wort, Enzalutamide Lumacaftor
¹ This is not an exhaustive list. Investigators should consult additional resources (e.g., website, drug label) for a full list or for more info on individual drugs.
² Refer to Flockhart Table™ for a more detailed list of CYP3A inducers and inhibitors (https://drug-interactions.medicine.iu.edu/Main-Table.aspx).

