5.4.3 Acalabrutinib

Acalabrutinib will be administered as a 100 mg tablet taken orally approximately every 12 hours. The tablets should be swallowed intact with water without being crushed, dissolved, broken, or chewed. Acalabrutinib can be taken with or without food.

If a dose is missed, it can be taken up to 3 hours after the scheduled time with a return to the normal schedule with the next dose. If it has been > 3 hours, the dose should not be taken and the participant should take the next dose at the scheduled time. The missed dose will not be made up and must be returned to the site at the next scheduled visit.

As acalabrutinib is metabolized by CYP3A, participants should be strongly cautioned against using herbal remedies or dietary supplements (in particular, St John's wort, which is a potent CYP3A inducer). Otherwise, subjects should maintain their regular diet unless modifications are required to manage an AE such as diarrhea, nausea, or vomiting.

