5.9.2 Precautionary and Prohibited medications/therapies

This is not intended to be an exhaustive list; the investigator should consider each concomitant medication and potential for drug-drug interactions.

- Prohibited from **Day 1 of protocol therapy until end of protocol therapy** (last day of study agent or decision to end study agent(s) whichever occurs later).
 - Herbal and natural remedies
 - Other investigational therapy
 - Other concurrent systemic anti-cancer therapy: chemotherapy, biological response modifiers, hormone therapy, surgery, palliative radiation therapy, or immunotherapy.
 - Live vaccines.
 - Systemic corticosteroid therapy at a daily dose ≥ 20 mg prednisone or equivalent. Patients may be using topical or inhaled corticosteroids.

- **Guidelines for co-administration with acalabrutinib:**

- Warfarin or equivalent Vitamin K antagonists are prohibited in patients on acalabrutinib as they may increase the risk of hemorrhage.
- Co-administration of acalabrutinib and a proton pump inhibitor should be avoided.
- Co-administration of acalabrutinib with a strong or moderate CYP3A inhibitor may increase acalabrutinib plasma concentrations resulting in increased toxicity. Use of strong or moderate CYP3A inhibitors should be avoided.
- Conversely, co-administration of acalabrutinib with a strong CYP3A inducer should be avoided as this may decrease acalabrutinib concentrations.

Refer to [Appendix E](#) for examples.

Refer to [Section 8.2.6](#) for appropriate acalabrutinib dose adjustments if co-administration with a CYP3A inhibitor or inducer is required.

If treatment with a gastric reducing agent is required, consider using a H2-receptor antagonist (e.g. famotidine) or an antacid (e.g. calcium carbonate).

- If receiving antacids, acalabrutinib dosing should be separated by at least 2 hours.
- If receiving H2-Receptor Antagonists, acalabrutinib should be taken 2 hours before taking a H2-receptor antagonist.

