8.2.6 Standard dose adjustments

Recommended guidelines if co-administration with a CYP3A inhibitor or inducer is unavoidable:

Dose Modifications for Acalabrutinib with concomitant CYP3A inhibitors or inducers		
CYP3A*	Co-administered Drug	Acalabrutinib Dose Modification
Inhibition	Strong CYP3A inhibitor	Avoid concomitant use. If these inhibitors will be used short-term (such as anti-infectives for up to 7 days), interrupt acalabrutinib.
	Moderate CYP3A inhibitor	100 mg once daily (QD)
Induction	Strong CYP3A inducer	Avoid concomitant use. If these inducers cannot be avoided, increase the acalabrutinib dose to 200 mg BID during concomitant administration with the strong inducer and return to the recommended dose of 100 mg BID after stopping the strong CYP3A inducer.

*Refer to [Appendix E](#) for examples of CYP3A inhibitors and inducers

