APPENDIX L-1: PATIENT DRUG DIARY INSTRUCTIONS

COH IRB number: 20459	Participant Initials (F, M, L) (if applicable):
Subject ID (issued by DCC):	Institution:

General Instructions:

1. Record the date and number of tablets that you took.
2. Record any comments, side effects, missed, vomited or skipped doses in the Comments column.
3. Bring this diary, all study drug bottles, and any unused tablets to each clinic visit. Do not throw away empty study drug bottles or unused tablets.
4. Do not share your drug supply or transfer it to any other container.

Umbralisib Specific Instructions:

- Take umbralisib **once a day within 30 minutes of starting a meal**, at approximately the same time each day.
- Tablets should be swallowed whole. The tablets should not be broken or chewed.
- If you miss a dose by **less than 12 hours**, take the missed dose right away. If you missed a dose by **more than 12 hours**, skip the missed dose and take the next dose at the usual time.
- If you vomit a dose, wait until the next scheduled dose; do not take extra medicine to make up the vomited dose.

Acalabrutinib Specific Instructions:

- Take acalabrutinib **twice a day (about 12 hours apart) with or without food**, at approximately the same time each day.
- Tablets should be swallowed whole. The tablets should not be opened, broken or chewed.
- If you miss a dose by **less than 3 hours**, take the missed dose right away. If you missed a dose by **more than 3 hours**, skip the missed dose and take the next dose at the usual time.
- If you vomit a dose, wait until the next scheduled dose; do not take extra medicine to make up the vomited dose.

Study Contact Information	
Study Doctor Phone: Name:	Study Nurse Phone: Name:

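### Section 5.4.3 and the patient instructions leave the regular diet unrestricted, while Appendix E classes three fruits as strong CYP3A inhibitors that Sections 5.9.2 and 8.2.6 say to avoid with acalabrutinib

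*Combined protocol and SAP*

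**What the plan says.** Five places in the combined protocol and SAP bear on this.

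- **Appendix E**, strong CYP3A inhibitor row: after a list of drugs, the row closes with "Cobicistat, Idelalisib, Grapefruit, Starfruit, Seville Oranges".
- **Section 5.9.2**: "Co-administration of acalabrutinib with a strong or moderate CYP3A inhibitor may increase acalabrutinib plasma concentrations resulting in increased toxicity". The next sentence reads "Use of strong or moderate CYP3A inhibitors should be avoided", and the section refers to Appendix E for examples.
- **Section 8.2.6**, for a strong CYP3A inhibitor: "Avoid concomitant use. If these inhibitors will be used short-term (such as anti-infectives for up to 7 days), interrupt acalabrutinib". The table's footnote also refers to Appendix E.
- **Section 5.4.3**: because acalabrutinib is metabolized by CYP3A, "participants should be strongly cautioned against using herbal remedies or dietary supplements", with St John's wort, an inducer, as the example. It continues: "Otherwise, subjects should maintain their regular diet unless modifications are required to manage an AE such as diarrhea, nausea, or vomiting".
- **Appendix L-1**, patient drug diary instructions: acalabrutinib is taken "twice a day (about 12 hours apart) with or without food". No food or interacting product is named.

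**The concern.** For three foods the protocol gives two instructions that do not fit together. Through the cross-references to Appendix E, 5.9.2 and 8.2.6 put grapefruit, starfruit and Seville oranges among the things to avoid. Section 5.4.3 deals with CYP3A in the same paragraph, names a narrower set of products, and tells participants to keep their usual diet apart from that set and apart from changes needed to manage an adverse event. A participant who regularly eats one of these fruits is, on the words of 5.4.3, told to carry on.

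What is at stake is participant safety and consistent conduct across sites. The protocol itself says that inhibition of this pathway may raise acalabrutinib concentrations and toxicity. A site that counsels from 5.4.3 and hands out L-1 may give different advice from a site that counsels from 5.9.2 and Appendix E. No endpoint definition, sample size or error rate is involved.

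**Working it through.** No arithmetic applies: the documents give no exposure ratio for these foods and no consumption rate. The check is a comparison of the passages.

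1. **Are the fruits inside the avoid rule?** Yes, by the protocol's own references. Appendix E classes them as strong inhibitors. Sections 5.9.2 and 8.2.6 state the rule for that class and both send the reader to Appendix E for its members. Section 5.9.2 is framed around medications and therapies, and the 8.2.6 table around co-administered drugs, but the appendix that both rely on includes the three foods without qualification.

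2. **Does the classification as strong matter?** Not for the conflict. Section 5.9.2 covers strong and moderate inhibitors alike, so moving the fruits to the moderate row would still leave 5.9.2 and 5.4.3 at odds.

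3. **Does 5.4.3 except the fruits from its diet sentence?** No. Its caution covers herbal remedies and dietary supplements. The diet sentence follows directly and has one exception, management of an adverse event. An ordinary fruit is neither a remedy nor a supplement.

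4. **Does another provision close the gap?**
   - The prohibited list in 5.9.2 includes "Herbal and natural remedies" but no food.
   - The exclusion criterion on strong CYP3A4 inhibitors and inducers (Section 3.2) concerns patients who need treatment with one, so it does not reach diet.
   - Section 5.9.1 asks sites to record added or changed concomitant therapy, including over-the-counter and alternative products; it does not mention food.
   - The Study Calendar (Section 10) has concomitant medication review and adverse event assessment, but no dietary question and no acalabrutinib pharmacokinetic sample.
   - The diary comments column (Appendices L-2 and L-3) asks about missed or vomited doses and side effects.

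5. **Does the patient sheet carry the rule?** No. The phrase in L-1 about food concerns taking a dose at or away from a meal. It does not itself conflict with Appendix E. The point about L-1 is only that it says nothing on the listed foods.

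So the fruits are named once, in an appendix whose footnote addresses investigators, while the administration section, read on its own, permits them.

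**The case against.** The best reply is that this is a loose general sentence and not a true opposition. A specific rule normally qualifies a general one. A site that reads the whole protocol will find the avoid rule, and a site that ignores 5.9.2, 8.2.6 and Appendix E is not complying with it. That has some force for sites. It has less for participants, who do not work from Appendix E. It is also weakened by where the diet sentence stands: directly after a CYP3A caution, so that it reads as saying what that caution leaves free.

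The reply is right about several stronger readings that a reader might infer.

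- **That L-1 is all the participant is told.** This cannot be shown. Consent pages were removed from the reviewed text, Section 17.4 describes a model consent with procedural and risk content, and 5.4.3 itself implies counselling by staff.
- **That the exposure would go unnoticed or unrecorded.** This is inference. A resulting adverse event would still be assessed, and what staff ask about diet cannot be seen from the documents.
- **That it would drive the accrual halt in Section 12.4.2.** That rule counts only listed severe events at least possibly related to treatment, among them grade 4 or higher infection, new-onset grade 4 atrial fibrillation and major hemorrhage. The first look halts accrual when more than 1 of the first 6 patients is affected. No figure links these foods to such events, and Section 14.1 has the investigator weigh other causes.
- **That the dose changes in 8.2.6 measure the dietary effect.** They are set for co-administered drugs and do not size the effect of a fruit.
- **That L-1 also contradicts the antacid and H2-antagonist spacing in 5.9.2.** It does not repeat that spacing, but nothing contradicts it. The eligibility criteria permit a switch from a proton pump inhibitor to those drugs and do not direct it.

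**Conclusion.** The inconsistency is real and should be corrected. Appendix E, 5.9.2 and 8.2.6 together say to avoid three named foods with acalabrutinib; 5.4.3 tells participants to keep their regular diet without excepting those foods; and L-1 does not mention them. A participant who follows 5.4.3 and L-1 could take acalabrutinib with foods the protocol elsewhere says to avoid.

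The size is unknown. The only statement of effect is the general one in 5.9.2 that concentrations may rise and toxicity increase. Nothing gives the magnitude for these fruits, the number of participants who eat them, or how often.

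The conclusion assumes that the references in 5.9.2 and 8.2.6 bring in every entry of the Appendix E row, foods included. A warning in the removed consent pages would reduce the practical risk, but it would not remove the disagreement between the protocol sections. The primary analysis and the two-stage design are unaffected.

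**What to change.** Reconcile 5.4.3 with 5.9.2, 8.2.6 and Appendix E so that a single rule covers the foods listed in Appendix E. Which rule that should be is for the sponsor to decide; this review proposes none. A cross-reference from the diet sentence in 5.4.3 to the agreed rule would be enough to make the sections consistent.

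Print the reconciled wording in the acalabrutinib part of Appendix L-1, and check that the consent form says the same. The existing antacid and H2-antagonist spacing from 5.9.2 may be repeated in L-1 as a convenience, since participants apply it at home, but that is optional.

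The cost is about one sentence in 5.4.3 and two or three lines in L-1 at the next amendment. No new procedure, visit or participant is needed.

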APPENDIX F: CORRELATIVE TISSUE FORM (FOR ALL SITES)

A copy of this form should accompany the sample shipments to [name] laboratory.

Non-COH sites: refer to [Appendix G](#) for shipping instructions.

COH IRB number: 20459	Shipping date (MM-DD-YYYY): _____/_____/_____
Subject ID (issued by DCC):	Participant Initials (F, M, L) (if applicable):
Institution:	
Date of collection/ biopsy (MM-DD-YYYY): _____/_____/_____	
Time point:  Baseline  Progression	
Diagnosis:	
Tissue type (FFPE scrolls, slides, biopsies):	
Number of scrolls:	Number of slides:

CRA/Study Coordinator/Nurse Printed Name:
CRA/Study Coordinator/Nurse Signature:
Contact Number:

APPENDIX G: TISSUE SHIPPING GUIDELINES TO [name]'S LABORATORY

*These guidelines apply to **non-COH sites** only.*

All biological material must be shipped according to applicable government and International Air Transport Association (IATA) regulations.

Shipping guidelines can also be found on the [FedEx website](#).

1. Aim to ship samples on a **Monday through Thursday**. If this is not feasible, advance arrangements should be made with [name] or his representative ([contact]).
2. Notify [name] or his representative ([contact]) of impending shipment. Sites must create their own FedEx shipping labels.
3. **Slides/ Blocks:** Batch ship at room temperature via FedEx. During extreme heat, include refrigerated (not frozen) gel packs or gel insulators.
It is recommended to ship samples via FedEx overnight (for a delivery by 3 pm or earlier the next day) or FedEx 2-day (with a morning delivery). During extreme heat, ship via FedEx overnight (for a delivery ideally by 10.30 am, or 3 pm the next day).
4. **Frozen samples** should be batch shipped on dry ice via FedEx overnight (for a delivery by 10.30 am the next day). The shipment should contain enough dry ice to last at least 72 hours.
5. On the day of shipment, email the sample shipment information to [name] or his representative ([contact]).
6. Ship samples with a copy of the correlative tissue form ([Appendix F](#)) and a copy of the pathology report to:

[name] MD, PhD
[name]
City of Hope National Medical Center
[name]
[name]
[contact]

APPENDIX H: CORRELATIVE BLOOD/ BONE MARROW COLLECTION FORM FOR NON-COH SITES ONLY

COH IRB number: 20459	Participant Initials (F, M, L) (if applicable):
Subject ID (issued by DCC):	Institution:

To be used by **non-COH sites** for the following blood/bone marrow samples being sent to **[name] lab**:

Blood Samples							
Blood Sample #	Time point of Collection	Expected Volume	Tube Type Used	Collected Volume	Time of Collection	Date of Collection	Indicate which sample was collected
1.	Cycle 1, Day 1	30 mL	Purple-top	____ mL	____:____ AM/ PM	____/____/____	
		Up to 10 mL	Cell-free DNA BCT	____ mL	____:____ AM/ PM	____/____/____	
2.	Cycle 2, Day 1	20 mL	Purple-top	____ mL	____:____ AM/ PM	____/____/____	
3.	Cycle 8, Day 1	20 mL	Purple -top	____ mL	____:____ AM/ PM	____/____/____	
		Up to 10 mL	Cell-free DNA BCT	____ mL	____:____ AM/ PM	____/____/____	
4.	Cycle 14, Day 1	20 mL	Purple -top	____ mL	____:____ AM/ PM	____/____/____	
		Up to 10 mL	Cell-free DNA BCT	____ mL	____:____ AM/ PM	____/____/____	
5.	EOM (End of maintenance)	20 mL	Purple -top	____ mL	____:____ AM/ PM	____/____/____	
		Up to 10 mL	Cell-free DNA BCT	____ mL	____:____ AM/ PM	____/____/____	
6.	At relapse	20 mL	Purple -top	____ mL	____:____ AM/ PM	____/____/____	
		Up to 10 mL	Cell-free DNA BCT	____ mL	____:____ AM/ PM	____/____/____	

Bone Marrow Samples						
Indicate which sample was collected	Time point of Collection	Expected Volume	Tube Type Used	Collected Volume	Time of Collection	Date of Collection
	Baseline	10 mL	Purple -top	____ mL	____:____ AM/ PM	____/____/____
	Suspected CR	10 mL	Purple -top	____ mL	____:____ AM/ PM	____/____/____
	Relapse	10 mL	Purple -top	____ mL	____:____ AM/ PM	____/____/____

A copy of this form should accompany the sample shipments to [name] lab.

Refer to the **blood/bone marrow shipping guidelines for shipping instructions (Appendix I)**.

CRA/Study Coordinator/ Nurse:	Contact Number:
CRA/Study Coordinator/ Nurse Signature:	Date:

APPENDIX I: BLOOD & BONE MARROW SHIPPING GUIDELINES TO [name]'S LABORATORY

*These guidelines apply to **non-COH sites** only.*

All biological material must be shipped according to applicable government and International Air Transport Association (IATA) regulations.

Shipping guidelines can also be found on the [FedEx website](#).

1. Aim to ship samples on a **Monday through Thursday**. If this is not feasible, advance arrangements should be made with [name] or his representative ([contact]). Sites must create their own FedEx shipping labels.
1. Blood/bone marrow samples in **purple-top tubes** will be sent **overnight at ambient temperature (15-25°C)** in an appropriate container via FedEx. Cell-free BCT tubes **should be shipped as soon as possible but no more than 3 days after being drawn** via overnight courier at ambient temperature. All tubes must be stored at room temperature while awaiting shipment as cold temperatures can affect future analyses.
2. **On the day of shipment**, email [name] or his representative ([contact]) the FedEx shipment #.
3. Ship samples with a **copy of the correlative blood/bone marrow collection form** ([Appendix H](#)) and a **copy of the latest CBC results (with differential)** and the **date of the test** to:

[name] MD, PhD
[name]
City of Hope National Medical Center
[name]
[name]
[contact]

APPENDIX J: HEPATITIS B SEROLOGIC TEST RESULTS

Interpretation of Hepatitis B Serologic Test Results

Hepatitis B serologic testing involves measurement of several hepatitis B virus (HBV)-specific antigens and antibodies. Different serologic "markers" or combinations of markers are used to identify different phases of HBV infection and to determine whether a patient has acute or chronic HBV infection, is immune to HBV as a result of prior infection or vaccination, or is susceptible to infection.

HBsAg anti-HBc anti-HBs	negative negative negative	Susceptible
HBsAg anti-HBc anti-HBs	negative positive positive	Immune due to natural infection
HBsAg anti-HBc anti-HBs	negative negative positive	Immune due to hepatitis B vaccination
HBsAg anti-HBc IgM anti-HBc anti-HBs	positive positive positive negative	Acutely infected
HBsAg anti-HBc IgM anti-HBc anti-HBs	positive positive negative negative	Chronically infected
HBsAg anti-HBc anti-HBs	negative positive negative	Interpretation unclear; four possibilities: 1. Resolved infection (most common) 2. False-positive anti-HBc, thus susceptible 3. "Low level" chronic infection 4. Resolving acute infection

Adapted from: A Comprehensive Immunization Strategy to Eliminate Transmission of Hepatitis B Virus Infection in the United States: Recommendations of the Advisory Committee on Immunization Practices. Part I: Immunization of Infants, Children, and Adolescents. MMWR 2005;54(No. RR-16).

■ **Hepatitis B surface antigen (HBsAg):**

A protein on the surface of hepatitis B virus; it can be detected in high levels in serum during acute or chronic hepatitis B virus infection. The presence of HBsAg indicates that the person is infectious. The body normally produces antibodies to HBsAg as part of the normal immune response to infection. HBsAg is the antigen used to make hepatitis B vaccine.

■ **Hepatitis B surface antibody (anti-HBs):**

The presence of anti-HBs is generally interpreted as indicating recovery and immunity from hepatitis B virus infection. Anti-HBs also develops in a person who has been successfully vaccinated against hepatitis B.

■ **Total hepatitis B core antibody (anti-HBc):**

Appears at the onset of symptoms in acute hepatitis B and persists for life. The presence of anti-HBc indicates previous or ongoing infection with hepatitis B virus in an undefined time frame.

■ **IgM antibody to hepatitis B core antigen (IgM anti-HBc):**

Positivity indicates recent infection with hepatitis B virus (<6 mos). Its presence indicates acute infection.

DEPARTMENT OF HEALTH & HUMAN SERVICES
Centers for Disease Control and Prevention
Division of Viral Hepatitis

www.cdc.gov/hepatitis

